#### V. Post-treatment Assessments at 3-Months and at 9-Months (Six-month follow-up)

At the conclusion of the 3-month intervention (post-treatment), or at the time a participant may drop out of the study (or in the rare instance of requiring additional or different anxiolytic treatment outside of our protocol), patients will complete the same clinical, biomarker, and psychometric test battery that they completed at baseline. At the 6-month follow-up, we will assess anxiety, patients' exercise habits, any psychiatric treatment, psychopharmacologic medications, aerobic fitness using a 6-minute walk test, and cardiac status, including revascularization procedures and CHD events. This will be a naturalistic follow-up that we have used in previous trials,[157, 158] which will allow us to determine patients' anxiety status 6 months after the conclusion of study-related treatment, along with changes in health habits and measures of quality of life. Figure 2 presents an expanded view of the assessment schedule and design of the study. For clinical events, we carefully will document cardiac-related hospitalizations and

emergency room visits, revascularizations, and any deaths for up to 4 years post-treatment.

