## **12. Data Management and Statistical Considerations**

**Data Analytic Approach.** The basic analytic strategy is a linear model carried out in the MPlus modeling software,[164] with treatment group contrasts as factors, and ethnicity, age, gender, and pre-treatment measure of the outcome variable as the adjustment covariables. The intent-to-treat principle (ITT) will be followed in all models, using full information maximum likelihood available in MPlus to manage missing data. For the case of the primary outcome, HADS-A, the model will include post-treatment HADS-A score as the response, with the predictors including two planned contrast variables representing 1) the two active treatments (exercise and escitalopram) vs. placebo and 2) exercise vs. escitalopram, with ethnicity, gender, age, and pre-treatment level of the HADS-A as the adjustment covariables. The contrast tests among treatment groups will be examined directly, i.e., no omnibus or “gateway” test will be required before interpreting them. In support of the HADS-A outcome, we also will compare the pattern of weekly changes in the STAI scores over time using a repeated measures model with Proc Mixed in SAS (SAS Institute, Cary, NC). The primary biomarker outcome, HRV, will be evaluated similarly. It is possible that a small number of participants may require off-protocol psychotropic medication during the course of the trial. These participants will be included in the ITT analysis and will not be replaced. We also will perform a sensitivity analysis with change in medication included as an adjustment variable in the statistical model. Finally, we will compare the treatments on the number of clinical events using a generalized linear model with the appropriate distributional form (e.g., negative binomial), using the same contrasts and covariates as in the linear model described above.

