
**13. Data and Safety Monitoring:** Study participants will be closely monitored for side effects, level of anxiety, and suicide risk. All patients will receive a weekly phone call to assess their state of anxiety using the STAI-State instrument. For patients who have a secondary diagnosis of MDD, BDI-II item #9 will be administered along with the 20-item STAI; patients who score  $>1$  on the item #9 of the BDI-II or who are judged to be at increased risk for suicidality will be evaluated by our study psychiatrist and referred for further treatment. For patients with a secondary diagnosis of MDD, suicidality will be assessed at each visit and by interim telephone contacts as needed. Subjects may experience no response to treatment or a worsening of symptoms; however, all subjects will be carefully monitored and withdrawn from the study if their symptoms worsen. If patients become suicidal, they will be evaluated by the treating psychiatrist

and appropriate referral or admission procedures will be initiated, such as to their referring physician or to the Duke Outpatient Affective Disorders Program, the Duke Psychology Clinic, or a local mental health center. Our study coordinator will contact the patient within 24 hours to make sure that he or she followed through with the referral. Furthermore, at the conclusion of the interventions, patients will be followed bimonthly via telephone and referred to their local physicians for further treatment, if necessary, or to the Outpatient Treatment Program at Duke University Medical Center or to the Duke Psychology Clinic.

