**Management of Worsening Depression or Active Suicidal Ideation:** In addition to weekly assessments, participants are advised to contact the study team should they believe their symptoms become worse or they develop active suicidal ideation. An interim visit or phone contact with [name] may be required. Patients who report suicidal ideation will be immediately evaluated by [name], the study psychiatrist. Patients who present with acute and active suicidal ideation will be terminated from the study and referred for further psychiatric care as needed.

**14. Privacy, Data Storage, and Confidentiality:** All participant data will be kept in locked offices and electronic data in password-protected folders on the shared drive that are only accessible to key personnel.

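### The FIML model for HADS-A leaves out the weekly STAI, so withdrawal for worsening can attenuate active vs placebo where no usable HADS-A is obtained

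*Combined protocol and SAP*

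**What the plan says.** **Primary model.** In Section 12 (Data Analytic Approach) "the model will include post-treatment HADS-A score as the response". The predictors are two planned contrasts, "with ethnicity, gender, age, and pre-treatment level of the HADS-A as the adjustment covariables". Missing data are handled by "using full information maximum likelihood available in MPlus to manage missing data". No auxiliary variable is named.

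**Weekly STAI-State.** Section 4, part I gives it two uses: following the process of change and picking out patients whose anxiety is worsening. Section 13 has every patient telephoned weekly for it. In the analysis it appears only in a supportive model: "we also will compare the pattern of weekly changes in the STAI scores over time using a repeated measures model".

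**Removal from the study.** Section 13 says that "all subjects will be carefully monitored and withdrawn from the study if their symptoms worsen". Its later paragraph on worsening depression and suicidal ideation adds: "Patients who present with acute and active suicidal ideation will be terminated from the study".

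**Assessment of those who leave.** Section 4, part V has the full baseline battery, which includes HADS-A, completed at 3 months "or at the time a participant may drop out of the study", or when other anxiolytic treatment becomes necessary. Section 12 adds that people who drop out voluntarily or cannot finish the protocol are not replaced and are still followed up, but gives no date. No section says whether a HADS-A taken at early exit serves as the post-treatment value.

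**The concern.** Naming FIML suggests that missing HADS-A scores will be dealt with using information already collected. As specified, the model has none to use. A patient with baseline data but no post-treatment HADS-A adds nothing to the treatment estimate, so the validity of that estimate rests on missingness depending only on arm and baseline covariates. Section 13 makes leaving depend on what happens during treatment.

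If active treatment works, which is the trial's own first hypothesis, placebo patients will tend to meet the worsening rule more often. Complete cases then drop more of the poor placebo outcomes, and the placebo mean looks better than it is. The contrast at stake is the one of primary interest, and it rests on 30 placebo patients.

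**Working it through.** **Inputs from the documents.** 150 randomized as 60:60:30 (Section 9). 15% attrition, model R² .20 and a target difference of .45 SD (Section 12, Power Analysis).

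**Inputs assumed.** No section gives withdrawal rates for worsening, so 5%, 10% and 15% overall were tried. No section gives the correlation between on-treatment STAI and final HADS-A after adjustment, so 0.4, 0.6 and 0.8 were tried. The share of withdrawn patients with a HADS-A was varied from 0 to 100%.

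**1. The plan's attrition figure.** 150 × .85 = 127.5, which agrees with the stated 127. Split 4:1, this is 101.6 active and 25.4 placebo. The standard error of the contrast is √.80 × √(1/101.6 + 1/25.4) = .894 × .222 = .198 SD, a yardstick for the losses below.

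**2. FIML against complete cases.** Section 9 places randomization after the baseline assessments, so covariates should be complete. The likelihood then splits into a part for the covariates and a part for HADS-A given covariates and arm. Patients without HADS-A contribute only to the first, which carries no information on the treatment coefficient. Numerical check with 150 patients and about 15% of responses missing: treatment coefficient −0.764188 by FIML and −0.764188 by complete-case regression.

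**3. No HADS-A on any withdrawn patient.** Simulated trials of 60:60:30 with a true effect of .45 SD and residual SD √.80. A STAI-like score carries the same treatment effect, and patients with the highest scores are withdrawn. At 5% overall, about 10% of placebo and 4% of active patients leave; at 15%, about 25% and 13%. Estimate from the planned model, and its share of the full-data estimate:

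| Residual correlation | 5% withdrawn | 10% withdrawn | 15% withdrawn |
|---|---|---|---|
| 0.4 | .412 (92%) | .404 (89%) | .380 (86%) |
| 0.6 | .397 (89%) | .370 (83%) | .353 (80%) |
| 0.8 | .383 (86%) | .351 (79%) | .335 (73%) |

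If withdrawal is triggered by the rise from baseline rather than by the level, the estimates run from .41 down to .31. Across both rules the loss is roughly 8–32%. The worst case, .45 − .31 = .14 SD, is about 0.7 of the standard error in step 1.

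**4. Some or all assessed at exit, with that score used as the outcome.** At correlation 0.6 and 15% withdrawn, the planned model gives .415 (92%), .435 (98%) and .453 (100%) when 50%, 80% and 100% are assessed. Over the whole grid, 80% capture gives .43–.44, a loss of about 1–4%. This step treats the exit score as if it were the 3-month score.

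**5. STAI added as an auxiliary.** When withdrawal depends on STAI alone, the estimate returns to the full-data value (.440–.460). When withdrawal also depends on HADS-A beyond what STAI carries, it improves but reaches only about .31–.43 of .45.

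**6. No true effect.** At 15% withdrawn and correlation 0.6, the planned model estimates .006 against .009 with full data, and the type I error is 5.1%.

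**The case against.** The strongest reply is that the plan does intend to have outcomes on people who leave: a full battery at dropout, and follow-up of those who cannot complete. If this works well and the exit score is used, step 4 shows almost nothing is lost. That stands, and it decides the size of the problem. It does not close it. An exit score may come weeks before 3 months, and whether it counts is unstated. The follow-up sentence covers voluntary dropouts and non-completers, and does not clearly reach patients whom the study withdraws.

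A reader might infer that the primary analysis will shrink the effect. The documents do not support that as a fact. The direction needs placebo patients to leave for worsening more often. Section 10 notes that SSRIs may worsen agitation, depression and suicidal ideation, and expects under 10% to drop out from side effects. If worsening withdrawals were about equal in active and placebo patients, the bias with no exit data falls to about 0–5% (correlation 0.6). Purely random loss of 10% on escitalopram changed nothing (89% with and without it, at 5% withdrawn and correlation 0.6).

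A reader might also infer that adding STAI cures the bias. It does so only when STAI alone decides who leaves. Section 13 sets no STAI threshold and also removes patients for suicidal ideation, which STAI does not measure.

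Finally, dropout is not ignored: Section 12 plans a CACE analysis and the STAI mixed model. The first targets the effect in adherers, and the second concerns a different outcome. Neither supplies missing HADS-A values under the primary estimand.

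**Conclusion.** The point holds in a conditional form. For any patient without a usable post-treatment HADS-A, the planned FIML model is a complete-case analysis that ignores the best available record of why the patient left. If treatment works and placebo patients leave more often for worsening, active versus placebo is attenuated: roughly 8–32% with no outcomes on withdrawn patients, and about 1–4% with 80% captured at exit and used. These figures rest on assumed withdrawal of 5–15% and residual correlation of 0.4–0.8, so they are a range of possibilities and not a forecast. A 15% rate of withdrawal for worsening would by itself use the plan's whole attrition allowance, so the upper end is an extreme case.

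The bias is conservative: it costs effect size and power and does not raise the false-positive rate. The change is worth making because the data are already collected and the use of exit scores has to be settled anyway.

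**What to change.** 1. **Section 12, Data Analytic Approach.** Name the weekly STAI-State scores, and any exit HADS-A, as auxiliary variables in the Mplus FIML model for HADS-A. Fix the set in advance, and say that this reduces the bias without removing it where withdrawal depends on things STAI does not capture, such as suicidal ideation.
2. **Section 4, part V, and the follow-up sentence in Section 12.** State that HADS-A is sought at the 3-month date from all randomized patients, including those who stop or are withdrawn. State that an exit score informs the 3-month value and does not replace it. The same rule should cover patients tested early because they need other anxiolytic treatment.
3. **Section 13.** Reconcile "withdrawn from the study if their symptoms worsen" with the continued assessment in Section 4, part V and Section 12, so that it is clear what data are still collected after removal. This concerns data collection only; the clinical criteria for removal are for the investigators.

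Optionally, add a sensitivity analysis that lets unobserved HADS-A scores be worse than the model predicts, since CACE does not serve that purpose.

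**Cost.** A few sentences, a little more analysis work with data already collected, and one extra questionnaire for each patient who leaves early.

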The purpose of this study is to evaluate the following hypotheses in a population of CHD patients with elevated symptoms of anxiety. The present study will examine the impact of a 3-month intervention of exercise, Lexapro, or placebo on anxiety symptoms and CHD biomarkers among individuals with cardiac disease and elevated anxiety. We hypothesize the following: (1) Both exercise training and medication will reduce anxiety symptoms to a greater extent than placebo; (2) Exercise training will improve CHD biomarkers of risk including autonomic regulation, vascular endothelial function, and inflammation more than either medication or placebo; and (3) Improvements in CHD biomarkers will be mediated by reductions in symptoms of anxiety. We also will explore potential moderators of treatment (e.g., anxiety diagnoses, CHD severity) as well as the longer-term benefits of treatment by documenting medical events and health care costs over a follow-up period of up to 4 years.

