**2/3. Medication/placebo.** Treatment in the medication and placebo pill arms will be supervised by [name]. Drug dispensing will be performed by licensed pharmacists at the Duke Investigational Drug Services, who have extensive experience in clinical trials. The pharmacists will maintain the blind and will dispense enough medication/placebo to last until the next visit. Each bottle will have a label displaying the dose and the subject ID number of the patient who is to receive the medication/placebo. We will use the SSRI escitalopram (Lexapro), which has received FDA approval for the treatment of anxiety, in 5 mg capsules or matched placebo. Medication will be dispensed as capsules of escitalopram or placebo in individually coded bottles. A new bottle of medications will be dispensed at each medication dispensing visit to study staff. Medication will be taken once daily in the morning but can be switched to once daily in the evening if deemed necessary. Medication adherence will be assessed using pill count at each study visit. Medication adherence, defined as the percentage of days on which the medication was taken, will be compared between the two pill arms to determine whether group differences in HADS-A scores could be attributed to differences in medication adherence.

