**Power Analysis.** Our study is powered with a focus on the primary hypothesis test: the treatment effect on anxiety as measured by HADS-A scores. We estimated power and sample size under the following assumptions: an alpha of .05, a linear model with age, gender, ethnicity, and baseline HADS-A score as covariates, a conservative estimate of the R-squared of .20 for the full model predicting post-treatment HADS-A, a 15% attrition rate, and two planned contrasts: active treatment vs. placebo and exercise vs. escitalopram. The comparison of primary interest will be active treatments vs. placebo. We estimate that a sample size of 150 (127 after attrition) will yield .80 power to detect at least a .45 SD difference between the active treatments and Placebo. In the general linear model, the exercise vs. escitalopram test will be only slightly less powered in being able to detect a .50 SD difference. In response to a previous reviewer comment, we believe that achieving this effect size is feasible. For example, in individuals with high anxiety sensitivity, Broman-Fulks[167] reported a .61 SD difference between exercisers and controls. We also re-examined data from a subset of highly anxious patients ( $STAI \geq 45$ ;  $N=32$ ) participating in our recently completed UPBEAT study[49] and found an effect size of .85 SDs on the STAI for both active treatments vs. placebo controls. We note that our power estimates are conservative in that the R-squared for the model is likely to be greater than .20 and dropout may be lower than 15%. With respect to the secondary outcome of HRV, our prior work showed that the R-squared between the baseline covariates and HRV was .73, greatly increasing the power of the tests of treatment on HRV. For the test of exercise vs. escitalopram on HRV, our primary CHD biomarker of interest, we will have a power of .80 to detect a .25 SD effect at alpha of .05. Finally, for our ancillary outcomes, including FMD, lipids, urinary catecholamines, and inflammatory markers, we have sufficient pilot data for FMD, which we use as an exemplar for power estimates: our earlier work showed that for FMD, the multiple R-squared between the baseline covariates (age, gender, ethnicity, and baseline FMD) and FMD was .50. Thus, we will have a power of .80 to detect a .34 SD effect for FMD with an alpha of .05. We estimate the power for the secondary analysis of treatment on time-to-clinical-event, assuming an event rate of 50% in the placebo group (based on unpublished data from our prior work[49]), 42 months for patient accrual, median follow-up time of 30 months and alpha = .05, is .80 to detect a reduction in event rate of 50% between both treatment groups and placebo, as well as .80 to detect a reduction in event rate of 56% between either intervention group individually and placebo. Unpublished data from our recently completed ENHANCED trial[168] revealed a 54% reduction in major adverse cardiac events among patients participating in CR compared to a matched control group of patients who did not participate in exercise-based CR.

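### Hypotheses 1 and 2 are worded arm by arm, but the plan lists no single-arm versus placebo test on HADS-A or HRV and no rule for claiming either hypothesis

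*Combined protocol and SAP*

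**What the plan says.** Section 2 (Purpose of the Study) states hypothesis 1 as "Both exercise training and medication will reduce anxiety symptoms to a greater extent than placebo" and hypothesis 2 as "Exercise training will improve CHD biomarkers of risk including autonomic regulation, vascular endothelial function, and inflammation more than either medication or placebo". Each therefore contains two comparisons.

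Section 12 (Data Analytic Approach) gives the HADS-A model "two planned contrast variables representing 1) the two active treatments (exercise and escitalopram) vs. placebo and 2) exercise vs. escitalopram". It adds that "The contrast tests among treatment groups will be examined directly", with no overall test first. For HRV it says only "The primary biomarker outcome, HRV, will be evaluated similarly".

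Section 12 (Power Analysis) repeats the two contrasts and says "The comparison of primary interest will be active treatments vs. placebo". Its HRV power statement covers one comparison: "For the test of exercise vs. escitalopram on HRV, our primary CHD biomarker of interest".

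Section 9 (Medication/placebo) says adherence "will be compared between the two pill arms to determine whether group differences in HADS-A scores could be attributed to differences in medication adherence". This presupposes an escitalopram versus placebo comparison on HADS-A that Section 12 does not list.

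**The concern.** Call pooled active versus placebo contrast 1, and exercise versus escitalopram contrast 2. Contrast 1 estimates the average of two arm effects, and a non-significant contrast 2 does not show that the arms are equal. Neither contrast, nor the pair, is a test that both arms beat placebo. For hypothesis 2, contrast 2 covers the medication half, but nothing listed covers exercise versus placebo.

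HRV carries the greater risk. Contrast 2 is positive if exercise raises HRV, and equally positive if exercise does nothing and escitalopram lowers it. Section 3 reports that SSRIs that inhibit norepinephrine reuptake reduce HRV, so the second possibility comes from the protocol's own background. Without a stated rule, a significant contrast 2 could be reported as exercise improving HRV.

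**Working it through.** **Inputs.** Allocation 60/60/30 (Section 9). Attrition 15%, alpha .05, R-squared .20 for HADS-A and .73 for HRV (Section 12, Power Analysis). Assumptions: attrition equal across arms, giving 51/51/25.5 retained; two-sided tests, since sidedness is not stated; a normal model with effects in outcome SDs. Joint probabilities come from 2,000,000 simulated trials per case.

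**Formula.** SE = sqrt(1 − R²) × sqrt(1/n₁ + 1/n₂).

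| Comparison | n | SE, HADS-A | SE, HRV |
|---|---|---|---|
| Contrast 1, pooled vs placebo | 102 vs 25.5 | .198 | .115 |
| Contrast 2, exercise vs escitalopram | 51 vs 51 | .177 | .103 |
| One arm vs placebo | 51 vs 25.5 | .217 | .126 |

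**The plan's own figures.** HADS-A contrast 2 at .50 SD: .50/.177 = 2.82, power about .80, as the Power Analysis implies. The pooled test at .45 SD gives .45/.198 = 2.27, power .62 against the stated .80 (.73 one-sided). HRV contrast 2 at .25 SD gives .25/.103 = 2.43, power .68 against the stated .80 (.78 one-sided). Those shortfalls are a separate matter; this point does not rest on them.

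**What the two contrasts identify.** With E, M and P the arm means, c₁ = (E + M)/2 − P and c₂ = E − M. Hence E − P = c₁ + c₂/2 and M − P = c₁ − c₂/2. Both arm effects are estimable from the planned model. But c₁ alone cannot distinguish arm effects of .45/.45 SD from .90/0 SD: its power is .62 in both cases.

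**HRV, exercise inert.** The chance that contrast 2 favours exercise is P(Z > 1.96 − d/.103), where d is the assumed escitalopram decrement.

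| d (SD) | Contrast 2 favours exercise | Exercise vs placebo favours exercise |
|---|---|---|
| 0 | 2.5% | 2.5% |
| .05 | 7% | 2.5% |
| .10 | 16% | 2.5% |
| .25 | 68% | 2.5% |
| .35 | 93% | 2.5% |

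Requiring exercise to beat both comparators gives a false claim in 1.2% to 2.5% of trials for d from .10 to .35. It can never exceed the 2.5% of the placebo comparison. One-sided at .05, the .25 SD row becomes 78% and 5%.

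**HADS-A, one arm inactive.** Contrasts 1 and 2 are independent because the active arms are equal in size. At .45/0 SD the pooled effect is .225: power .205, with contrast 2 power .719. Pooled significant and contrast 2 not: .205 × (1 − .719) = .058, or 6%. At .61/0 SD it is 2%; at .85/0 SD, 0.1%. With the pooled test one-sided and contrast 2 two-sided, the first two become 9% and 3%.

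**Power of the added claims.** Detectable effect at .80 power is (1.96 + .84) × SE: .61 SD versus placebo for HADS-A and .35 SD for HRV. Both arms beating placebo on HADS-A at .45 SD each: .41, against .62 for the pooled test. Exercise beating both comparators on HRV at .25 SD, with escitalopram equal to placebo: .41, against .68 for contrast 2 alone.

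**The case against.** The arms and directions are already fixed in Section 2, and the model, covariates and missing-data method in Section 12. Since the arm effects follow from the two contrasts, a reader might infer too much in saying that hypothesis 1 could be tested only by a choice made after the data are seen. The documents do not support that. What is missing is the contrast lines and the decision rule.

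A reader might also infer that the pooled primary test is wrong. It is not: the plan names it as the comparison of primary interest and may do so.

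The HRV scenario is an assumption on both sides. Section 3 cites trials in which exercise improves HRV, including in CHD patients. Its warning concerns SSRIs that inhibit norepinephrine reuptake, and Section 10 describes escitalopram as among the more selective agents. The documents therefore do not show that escitalopram will lower HRV by .25 SD, or at all. Hence the range from zero.

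The HRV sentence lists no contrasts and directly follows the repeated-measures sentence on STAI. Reading it as the same two contrasts is an inference, supported by the HRV power statement for contrast 2.

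Two passages might seem to fill the gap. The mediation model in Section 12 contrasts the active groups with placebo, and its treatment-to-anxiety path could be arm by arm. But the wording is ambiguous, and the model is introduced as additional to treatment effects. The Power Analysis compares each arm individually with placebo, but only for clinical events. The mismatch there between a count model and a time-to-event power statement is a separate issue.

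These objections limit the size of the point; they do not supply the missing tests or rule.

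**Conclusion.** The point holds as a gap between the stated hypotheses and the listed tests, worth fixing before analysis. It does not invalidate the primary test. The consequence is mainly for HRV: crediting exercise from contrast 2 alone is wrong in 2.5% to 93% of trials as the assumed escitalopram decrement goes from 0 to .35 SD with exercise inert. For HADS-A it is largely a wording mismatch, with at most 6% of trials affected at the effects examined (two-sided), because contrast 2 exposes most cases of one inactive arm. The figures assume 2:2:1 allocation, equal 15% attrition, the plan's R-squared values and two-sided .05.

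**What to change.** Keep pooled active versus placebo as the primary test. For HADS-A and HRV, pre-specify exercise versus placebo and escitalopram versus placebo from the same fitted model, reported with 95% confidence intervals, and state that HRV uses these contrasts.

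- **HRV:** claim hypothesis 2 only if exercise beats both escitalopram and placebo. Report escitalopram versus placebo so that any decrement is visible.
- **HADS-A:** claim that both treatments work only if each beats placebo. Alternatively, reword hypothesis 1 to match the pooled test and label the arm estimates descriptive.
- **Optional gate:** the HADS-A arm tests may be made conditional on a significant pooled test. The claim for both arms loses nothing: two differences each above 1.96 × .217 = .425 have a mean above 1.96 × .198 = .388. With both arms null, familywise error for the arm-versus-placebo tests is .047, against .085 ungated. This does not cover contrast 2, which stays ungated; the two planned contrasts together give 1 − .95² = about .098. The gate also cuts power for a single active arm at .45/0 SD from .55 to .20. If used, say that it applies only to the added tests, since Section 12 otherwise requires no gateway.

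The cost is SAP wording and a few contrast statements, with no change to sample size, data collection or the primary test. The SAP should state the lower power of the two-part claims (.41 in each case) and the detectable effects against placebo.
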